## 7) Recruitment Methods

Investigators will recruit participants from among their own patients. All patients who meet the inclusion/exclusion criteria will be enrolled. We are requesting waiver of consent.

## 8) Study Timelines

- Duration of individual patient participation: Patients will participate from the time when they are brought into the OR preoperative suite and it is determined they will have an endotracheal tube (ET) or laryngeal mask airway (LMA) placed. The study observation period will end once the airway has been secured.
- The duration anticipated to enroll all study subjects will be sufficient time to enroll the target sample of patients.
- An interim analysis will be conducted halfway through enrollment of the with-cannula group.
- The estimated primary analysis will be done by December 2016.

## 9) Study Endpoints

As this study is of minimal intervention and minimal risk, we do not anticipate early study termination for research-induced adverse outcomes. The planned intervention may be suspended or canceled after the interim analysis if it is ineffective, or if we reach statistical significance on the primary outcome halfway through collecting our estimated number of patients. “Ineffectiveness” is defined here as a failure to identify one-tailed superiority of the with-cannula group with  $p < 0.20$  on *any* of the outcomes (primary or secondary) at the interim analysis.

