## 5) Inclusion and Exclusion Criteria

The study population would be infants and children with adjusted gestational age of 40 weeks or greater to 8 years of age, scheduled for surgery at UNM. Patients to be excluded would be premature infants with adjusted gestational age of less than 40 weeks, those undergoing mask ventilation, and patients with ASA class 4-6. Enrollment would occur for up to six months after HRRC approval and study commencement.

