## 6) Number of Subjects (Recruitment Target)

A sample size estimate based on prior studies of apneic oxygenation in adults indicates that approximately 400 subjects would be appropriate for this study, 200 in the baseline group without nasal cannula adjunct and 200 patients with implementation of nasal cannula adjunct during the peri-intubation period.

A power analysis (based on formulae in *Statistics in Medicine* 1982; 1:121-9) indicated that if the baseline rate of reaching 95% SPO2 is 15% of patients and this procedure reduces that rate by half, 80% power at  $\alpha=0.05$  is reached for a one-tailed logrank test with a total of 371 patients. Rounding up to 400 patients to accommodate incomplete datasheets would provide power of 94%.

Based on enrollment rate to date, we estimate that enrollment of 400 patients will take approximately one year. Because the planned evaluation of routine use of nasal cannula adjunct oxygenation is occurring independent of enrollment counts to the baseline study condition, data

may be gathered on more than 200 patients in that group. In order to permit analysis without loss of power, we may need to enroll a higher total sample size in order to achieve an equal sample size in the group with the cannula. To accommodate this reality, we may enroll a maximum of 500 patients in the entire study.

This period will also permit education of all relevant providers and staff on the use of peri-intubation nasal cannula oxygenation.

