## 11) Study Methods

This is a prospective observational study. Prospectively-recorded data are necessary because data on the outcomes of interest are not available in the medical record.

Participants will be enrolled in the study once they have entered the pre-operative area and they are determined by the attending anesthesiologist to

that they are an eligible study participant. Participants enrolled in the first three months of the study will be assigned to the baseline condition as described below. Participants enrolled in the second phase of the study will be assigned to the with-cannula condition described below.

A patient sticker will be added to the data collection form. Basic demographic information and vitals will be recorded before premedication is administered as is standard at entry to the pre-operative area. Timing devices of the same make and model will be used consistently between all study cases.

For the **baseline group** of this observational study, all intubation procedures will be performed as per usual practice. Patients will receive premedication as determined by anesthesiologist/resident/midlevel, and the type and dose will be recorded.

Once patients are brought to the operating room suite and vital signs are being monitored, patients will be preoxygenated via mask per standard of care, with an expired oxygenation concentration minimum of 0.75. Vitals will be recorded at the moment prior to removal of the face mask at the end of the preoxygenation period. Anesthetic induction will then be performed with agents and dosages as per the provider's clinical judgment.

Airway management consisting of oral endotracheal intubation or laryngeal mask airway insertion will take place. As per usual practice, an attending physician who is expert in pediatric airway management will supervise the procedure and intervene before the patient experiences excessive oxygen desaturation. The lowest oxygen saturation and the time to either successful intubation or intervention by an attending physician will be recorded.

For the **with-cannula group**, all of the above steps will be maintained. The sole difference will be nasal cannula placement after induction. It will be set to deliver 5L of oxygen per minute.

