**14) Data Management**

Only study investigators will have access to study data. Study participants will be assigned a study number, and this number will be used in all data analyses. The data will be entered into an electronic database that will be stored on UNMHSC password-protected servers. The electronic data will only have study participant numbers and no identifiers that could link specific patients to the data. All data forms that bear identifiers will be securely destroyed (shredded) upon application to HRRC for study closure, so that only deidentified data remain when that application is made.

As noted above, data to be gathered include basic demographic data, data about the anesthetic induction procedure, and data about the patient's O2 saturation.

Routine demographic data will be analyzed with t-tests and Wilcoxon rank-sum tests, as appropriate depending on normality of data distributions. Categorical data will be analyzed with appropriate analyses, such as chi-square, Fisher's exact, risk ratio, and/or odds ratio.

The primary outcome of time to cross the 95% saturation threshold will be analyzed with Kaplan-Meier curves and survival analysis with "censoring" for cases in which the threshold was not crossed because of either successful intubation or intervention by the attending physician.

Secondary outcomes with continuous data (e.g. the lowest observed O2 saturation) will be analyzed with standard t-tests or Wilcoxon rank-sum tests, as appropriate depending on normality of data distributions. Secondary outcomes with binary data (e.g. whether intervention by the attending physician is required) will be analyzed with chi-square or Fisher's Exact tests as appropriate depending on cell counts.

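### The interim rule for significance on the primary outcome has no level, direction or matching final level; one-tailed 0.05 at both looks would give a type I error of about 7.4%, not 5%

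*Combined protocol and SAP*

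**What the plan says.** - **Section 8 (Study Timelines)** plans one interim look: "An interim analysis will be conducted halfway through enrollment of the with-cannula group".
- **Section 9 (Study Endpoints)** gives two grounds for suspending or canceling the intervention after that look. One is ineffectiveness, which has a number and a direction: no outcome shows one-tailed superiority at p < 0.20. The other is "or if we reach statistical significance on the primary outcome halfway through collecting our estimated number of patients", which has neither. Both are permissive (may).
- **Section 6 (Number of Subjects)** holds the only level for the primary outcome. It sets α = 0.05 and says 80% power "is reached for a one-tailed logrank test with a total of 371 patients". It plans 200 patients per group. If the baseline group runs over 200, the cannula group is to be enlarged to match, and "we may enroll a maximum of 500 patients in the entire study".
- **Section 11 (Study Methods)** enrolls the baseline group first and the with-cannula group second.
- **Section 14 (Data Management)** states that "The primary outcome of time to cross the 95% saturation threshold will be analyzed with Kaplan-Meier curves and survival analysis". It mentions no interim look, no final significance level and no adjustment.

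**The concern.** A rule that acts on significance halfway, followed by a final test of the same hypothesis, gives the primary outcome two chances to succeed. Unless the two levels are chosen together, the overall false-positive rate exceeds the level at which each test is run. Here the interim level is missing, and the only level available to fill the gap was set for a single test.

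The consequence is practical. If the interim result is called significant, a reader cannot tell what threshold it had to pass. If the study runs to the end, a reader cannot tell what level applies to the final logrank test. The contrast within section 9 sharpens the point: the ineffectiveness rule has both a p-value and a direction, and the significance rule beside it has neither.

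**Working it through.** **1. The plan's own figure.** Inputs from section 6: one-tailed 0.05, 80% power, 15% of baseline patients reaching the threshold, halved by the cannula (ratio 0.5). A logrank events formula gives (1.645 + 0.842)² × (1.5/0.5)² = 55.64 events, and 55.64/0.15 = 370.95, so 371. This reproduces the stated total. It also confirms that the design level is one-tailed 0.05 spent on a single test.

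**2. Information fraction at the interim look.** Let nb be the baseline size, n1 the cannula patients at the look and n2 the cannula patients at the end. Then

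t = (1/nb + 1/n2) / (1/nb + 1/n1).

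The baseline group is complete at the look (section 11), the look comes at half the cannula group (section 8), and the groups end equal (section 6).
- 200 + 100, then 200 + 200: t = (1/200 + 1/200)/(1/200 + 1/100) = 0.010/0.015 = 2/3.
- 250 + 125, then 250 + 250: t = 0.008/0.012 = 2/3.

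For any equal final size n, t = (2/n)/(3/n) = 2/3, so the result does not depend on whether the study ends at 400 or at the cap of 500.

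**3. Type I error.** Treat the two logrank statistics as bivariate normal with correlation √(2/3) = 0.816. The error is 1 − P(Z1 < c1, Z2 < c2).

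| Interim level (one-tailed) | Final level (one-tailed) | Type I error |
|---|---|---|
| 0.05 | 0.05 | 7.42% |
| 0.025 (two-tailed 0.05) | 0.05 | 5.86% |
| 0.001 | 0.05 | 5.00% |
| 0.0164 | 0.0451 | 5.00% |

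The last row is the Lan-DeMets O'Brien-Fleming-type boundary at t = 2/3.

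**4. Check by simulation.** Null logrank data were simulated with a 15% event rate and exponential event and censoring times. At 200 + 100 then 200 + 200 (100,000 runs), either look was significant in 7.3% of trials, against 5.0% for the final test alone. A separate simulation (60,000 runs) gave 7.1% at that schedule and 7.4% at 250 + 125 then 250 + 250.

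**5. Does the ineffectiveness rule offset this?** If it were always obeyed and applied to the primary outcome alone, the error would be 6.95%. That is a lower limit, because section 9 makes the rule optional and any one outcome can satisfy it.

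**6. Cost of a boundary.** Use the drift that gives a single final test 80% power: 1.645 + 0.842 = 2.486 before rounding. The mean of Z1 is then 2.486 × 0.816 = 2.03.

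| Rule | Chance of crossing at the interim | Overall power |
|---|---|---|
| 0.05 unadjusted | P(Z > 1.645 − 2.03) = 65% | not comparable (error 7.4%) |
| 0.0164 then 0.0451 | P(Z > 2.135 − 2.03) = 46% | 79.3% |
| 0.001 then 0.05 | P(Z > 3.090 − 2.03) = 14% | 80.0% |

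Simulation of 15% against 7.5% at 200 + 100 then 200 + 200 (40,000 runs) gave crossing rates of 64%, 42% and 9%.

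**The case against.** **The inflation is conditional.** Section 9 does not say that 0.05 applies at the interim. It speaks of suspending or canceling the intervention, not of declaring success. If significance means two-tailed 0.05, the excess shrinks to under one point; if the rule is meant only against the cannula, there is none. This stands, and the 7.4% must carry its assumptions. It does not remove the gap, because the text does not let a reader choose among these readings.

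**A reader might infer a wider range of error rates, from 6.9% to 7.8%.** Section 11 says "Participants enrolled in the first three months of the study will be assigned to the baseline condition", while section 5 says "Enrollment would occur for up to six months after HRRC approval and study commencement" and section 6 says "we estimate that enrollment of 400 patients will take approximately one year". At steady accrual, three months is 400 × 3/12 = 100 baseline patients on the one-year estimate, and a look at 100 + 150 of a final 100 + 300 gives 6.9%. At the other end, a look at 250 + 100 of a final 250 + 250 gives 7.8%. The documents set out neither schedule. Section 6 foresees 200 or more baseline patients and equal groups, and half of a 250-patient cannula group is 125, not 100.

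**A reader might also infer that the time of the look is open.** Half of 400 patients, taken literally with 200 enrolled at baseline first, leaves no cannula patients and nothing to compare. That cannot be intended. Section 9 refers to the interim analysis, and section 8 defines only one. The wording in section 9 is loose and should be aligned, but section 8 fixes the timing.

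**The study is a non-randomised before/after comparison.** Confounding by time may well matter more than two extra points of nominal error, and nothing here addresses it. That limits the weight of the point. The plan nevertheless sets a level and a stopping rule, and the two should agree.

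**Conclusion.** The concern holds in a conditional form. The plan has an interim significance rule without a level or direction, and no matching final level. Applying its only stated level at both looks gives a type I error of about 7.4%, an excess of about 2.4 percentage points over 5%. That figure rests on four assumptions:
- one-tailed 0.05 toward superiority is used at both looks;
- an interim success is reported as positive;
- the look takes place when section 8 says;
- the groups end equal, as section 6 intends.

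The documents do not show that the study's error rate is in fact 7.4%, nor whether the look has already been made. The point should be fixed: it concerns the decision rule for the primary outcome, and the repair is a few sentences.

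**What to change.** In section 9, state the direction of the rule and a numeric one-tailed interim level for the primary outcome. In section 14, state the matching final level. Any of these would do:
- **Interim p < 0.001, final 0.05.** Type I error 5.0%, power 80.0%; about a 14% chance of crossing early under the design effect.
- **Lan-DeMets O'Brien-Fleming-type boundary**, recomputed at the actual information fraction; at 2/3 it is 0.016 then 0.045. Type I error 5.0%, power 79.3%; about a 46% chance of crossing early.
- **No efficacy claim from the interim look**, with the final test kept at 0.05. No loss of power, but early stopping for efficacy is given up.

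Align the timing phrase in section 9 with section 8 and give the expected number in each group at the look. If the look has already been made, report the level that was used.

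No extra patients or data are needed. The cost is the lower chance of stopping early, against about 65% with unadjusted 0.05.

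### The interim look allows an efficacy stop with no stated significance level or adjusted final level; one-tailed 0.05 at both looks gives about 7.4% type I error, not 5%

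*Combined protocol and SAP*

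**What the plan says.** - **Timing.** Section 8 (Study Timelines): "An interim analysis will be conducted halfway through enrollment of the with-cannula group".
- **Efficacy stop.** Section 9 (Study Endpoints) says the intervention may be halted for ineffectiveness "or if we reach statistical significance on the primary outcome halfway through collecting our estimated number of patients". It does not say what level counts as significant.
- **Futility.** Section 9 does put a number on ineffectiveness: "a failure to identify one-tailed superiority of the with-cannula group" at p<0.20 on every primary and secondary outcome.
- **Level.** Section 6 (Number of Subjects) has the only alpha in the document: "80% power at $\alpha=0.05$ is reached for a one-tailed logrank test". It belongs to a single-test sample-size calculation.
- **Analysis.** Section 14 (Data Management) specifies Kaplan-Meier curves and survival analysis for the primary outcome. It gives no alpha, sidedness, interim boundary or final level.
- **Enrolment order and size.** Section 11 (Study Methods): "Participants enrolled in the first three months of the study will be assigned to the baseline condition as described below". Section 6 adds that baseline data "may be gathered on more than 200 patients in that group" and that "we may enroll a maximum of 500 patients in the entire study".

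**The concern.** The primary outcome can be declared significant on either of two occasions, but the plan states a level suited to one. Testing accumulating data twice at the same level raises the chance of a false claim above that level. Because futility is defined numerically and efficacy is not, the interim threshold is also open to choice once the data are known.

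The rule would often decide the study. Under the plan's own assumed effect, unadjusted testing at 0.05 would cross at the interim about 59-60% of the time, and the claim would then rest on about 100 cannula patients.

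**Working it through.** **Inputs.** One-tailed 0.05 (section 6), critical value 1.645. One interim look and one final analysis (section 8). Groups of 200 and 200 (section 6), with baseline patients enrolled first (section 11), so the baseline group is complete when half the cannula group is in.

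**The plan's own figures.** Section 6 implies a 5% error but shows no two-look calculation to reproduce. Its sample size was recalculated for reference. For 15% vs 7.5%, one-tailed 0.05 and 80% power, standard formulas give totals of about 409 to 498 rather than 371, and power at 400 of about 72-79% rather than 94%. That is a separate matter: the type I error below depends only on the test levels and the information fraction.

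**Information fraction.** Information is proportional to n1·n2/(n1+n2).

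| Interim | Final | Interim information | Final information | t |
|---|---|---|---|---|
| 200 vs 100 | 200 vs 200 | 66.7 | 100 | 0.667 |
| 250 vs 125 | 250 vs 250 | 83.3 | 125 | 0.667 |
| 300 vs 100 | 300 vs 200 | 75 | 120 | 0.625 |

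The last two rows reach the cap of 500.

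**Type I error at 0.05 twice.** Under the null, the two logrank statistics are approximately bivariate normal with correlation √t, which is 0.816 at t = 0.667.

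P(any rejection) = P(Z1 > 1.645) + P(Z1 ≤ 1.645, Z2 > 1.645)

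- t = 0.667: 0.0500 + 0.0242 = **0.0742**
- t = 0.625: 0.0500 + 0.0258 = **0.0758**

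Logrank simulations for 200 vs 100 then 200 vs 200 gave 0.0735 (100,000 runs) and 0.0738 (40,000 runs). Across all simulations of the 200/200 and 300/200 cases the range was about 7.1% to 7.5%, so differences between those scenarios should not be stressed.

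**Effect of the futility rule.** If it were binding and judged on the primary outcome alone, the study would continue only when 0.842 < Z1 ≤ 1.645. The error would be 0.0695 at t = 0.667 and 0.0698 at t = 0.625. The written rule is optional and requires failure on every outcome, so it lowers the error less than this.

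**If a stricter interim level was meant**, with the final test left at 0.05 (t = 0.667):

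| Interim level | Overall error |
|---|---|
| 0.025 | 0.0586 |
| 0.01 | 0.0520 |
| 0.001 | 0.0500 |

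**A boundary that holds 5%.** With Lan-DeMets O'Brien-Fleming-type spending, the interim level is 2[1 − Φ(1.960/√t)], and the final level is solved so that the total is 0.05.

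- t = 0.667: 2[1 − Φ(2.400)] = 0.0164; final 0.0451
- t = 0.625: 2[1 − Φ(2.479)] = 0.0132; final 0.0460

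Simulated error with the first pair was 0.0495.

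**Power under 15% vs 7.5%, 200 vs 200** (100,000 simulated logrank trials; in brackets, the normal approximation anchored at 77.7% single-test power):

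| Rule | Power | Crosses at interim |
|---|---|---|
| Single test at 0.05 | 0.775 (0.777) | not applicable |
| 0.05 at both looks | 0.801 (0.806) | 0.600 |
| 0.0164 then 0.0451 | 0.766 (0.770) | 0.378 |

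A two-proportion formula gives interim crossing of 0.591 and 0.377.

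**The case against.** The strongest reply is that 7.4% describes a rule the plan never writes down. Section 9 does not attach 0.05 to the interim look, and an intended level of 0.01 or 0.001 would leave the error at 5.2% or 5.0%. The stop is also optional, and nothing says that an interim crossing counts as the study's positive result; if only the final test were ever used for the claim, the error would stay at 5%. The excess is about 2.4 percentage points in a single-centre, minimal-risk comparison of consecutive periods, where confounding by period could produce an apparent benefit that no boundary prevents. Section 26 adds that the change to cannula use will happen whatever this study finds.

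Much of this is fair as a limit on weight. The 7.4% is conditional, and the before/after design is left untouched. But the natural reading is that significance means the one level the document states, and ending the intervention at the interim ends cannula accrual, which makes the interim result the final one. If a stricter level was intended, it still needs to be written down. A different weakness in the design does not excuse an undefined stopping rule.

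It is also true that O'Brien-Fleming-type spending is one valid choice among several, and that controlling the type I error does not require the stop to be mandatory.

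**Conclusion.** The concern holds. The plan allows an efficacy stop on the primary outcome without an interim level or an adjusted final level. On the natural reading the one-tailed type I error is about 7.4%, and up to about 7.6% by normal approximation with 300 baseline and 200 cannula patients, against 5% intended.

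This assumes one-tailed 0.05 at both looks, a complete baseline group at the interim, and that an early crossing is acted on and reported as superiority. The inflation is modest, but the plan should correct it because doing so costs little.

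**What to change.** Add one or two sentences to section 9:

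- The primary logrank test is controlled at an overall one-tailed 0.05 by Lan-DeMets spending of O'Brien-Fleming type, with nominal levels of 0.016 at the interim and 0.045 at the end for 200 vs 100 then 200 vs 200.
- The levels are recomputed from the actual group sizes; for 300 baseline and 200 cannula patients they are 0.013 and 0.046.
- Crossing the boundary stops data collection. This makes the consequence of the rule clear, although error control does not depend on it.

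Any other prespecified boundary that holds 5% would also answer the point. An interim level of 0.001 with the final test at 0.05 is the simplest, at the price of rarer early stopping.

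No new data are needed. With the proposed boundary, power is about 77%, against about 78% for a single test and 80-81% for unadjusted testing, part of which is bought by the excess type I error. The real cost is that the chance of an early stop falls from about 59-60% to about 37-38%, which is acceptable for an intervention the protocol describes as minimal risk.
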